8.2. Monitoring Populations and Collaborative Hospitals

8.2.1. Subject selection

A subject will be eligible for inclusion in this study only if all of the following criteria apply:

I. Informed consent

An appropriately signed and dated assent must be obtained from the parent/guardian of the subject.

II. Age

1 to <4 years of age at Visit 1.

III. Flixotide 50 µg treatment

Subjects who have been prescribed Flixotide 50 µg for a medically appropriate use for the first time will be included in this observational program. Flixotide 50 µg therapy should be in line with the approved dosing: 50 to 100 µg twice daily. Subjects should have the ability to inhale the doses via a paediatric spacer with a face mask appropriately. Subjects who have been exposed to Flixotide 50 µg, 125 µg and 250 µg treatment previously will not be included.

IV. The parent/guardian of the subject must provide reliable contact information which includes home phone or cell phone for the follow up visits.

V. The parent/guardian of the subject must have the ability to comply study procedures.

Specific information regarding warnings, precautions, contraindications, adverse events, and other pertinent information on Flixotide 50 µg that may impact subject eligibility is provided in the approved product label.

8.2.2. Subject Withdrawal

A subject and their parent/guardian may withdraw consent to have their data collected in the program at any time. If this occurs, they must be withdrawn from this study. Data collected until the point of consent withdrawal will be used.

8.2.3. Collaborative Hospitals

This post-marketing program is planned to recruit paediatric subjects from 3 to 5 hospitals (may be adjusted as per recruitment progress) in China.

8.3. Study size

It is planned to include 150 asthmatic subjects, aged 1 to 4 years who have been prescribed Flixotide 50 µg treatment for appropriate medical use for the first time in China.

8.4. Data collection

The information of the subjects' demographic factors, medical history, Flixotide 50 µg therapy, concomitant medications, AEs and SAEs, will be collected. Paper diary cards will be dispensed at Visit 1 for the parent/guardian of the subject to record Flixotide 50 µg therapy, concomitant medication, AEs and SAEs. The investigator will record the source information in the medical records by asking the parent/guardian of the subject during the follow-up on site or telephone visits.

Subjects' data will be entered into GSK defined eCRFs.

No data will be collected on subjects until consent for data collection has been obtained in line with local ethical standards for observational program.

8.5. Data management

8.5.1. Data handling conventions

Management of clinical data will be performed in accordance with applicable GSK standards and data cleaning procedures to ensure the integrity of the data. Adverse events and concomitant medications terms will be coded using Medical Dictionary for Regulatory Activities (MedDRA) and, World Health Organisation (WHO)Drug. CRFs including queries and audit trails will be retained by GSK, and copies will be sent to the investigator to maintain as the investigator copy. Subject initials will not be collected or transmitted to GSK according to GSK policy.

8.5.2. Timings of Assessment during follow-up

Visit 1 will be defined as baseline. Follow-up visits will be performed at 4 weeks and 12 weeks since baseline visit. There is ± 3 day window period for every follow up visit.

8.6. Statistical analysis

8.6.1. Hypotheses

This is a post-marketing observational study. A descriptive approach will be used and no formal inference is planned in this study. Some justification is provided as follows.

8.6.2. Sample Size Consideration

Considering that Flixotide is an established brand, which has been in the China market for more than 10 years, it is more sensible to consider drug related AE (adverse drug reaction, ADR) instead of any specific rare case.

Based on global phase III studies FAS30007 [GlaxoSmithKline Document Number [GM2001/00151/00](#)], FAS30030 [GlaxoSmithKline Document Number [RM2004/0187/00](#)] and FAS30009 [GlaxoSmithKline Report Number [GM2001/00103/00](#)] on 1 to <4 years old, the smallest incidence rate of ADR in a given study was 3%. The Japanese post market safety survey reported the ADR rate as 1.68%. Taken the lowest estimate between two approaches, assuming the ADR rate in Chinese 1 to <4 year old children patients is not lower than 1.5%, it is calculated that a study with 150 subjects will have approximately 90% probability to observe at least one ADR.

8.6.3. Data Analysis Consideration

The safety population is defined as all included subjects who received at least one dose of Flixotide 50 μ g and complete one follow up visit, including scheduled or unscheduled visit. Subjects who retrospectively received will also be included in.

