7. RESEARCH QUESTION AND OBJECTIVE(S)

The data obtained from this post-marketing program will further enhance and supplement the currently available safety data from clinical trials as well as provide more detailed information than that obtained typically available through routine spontaneous adverse event reporting, thus justify the safety use of Flixotide 50 µg inhaled via a paediatric spacer device with a face mask in Chinese children aged 1 to <4 years old.

The objective of this program is to evaluate the post-marketing safety profile of Flixotide 50 µg in patients aged 1 to <4 years. The adverse drug reactions and predictors of these adverse reactions among patients will be observed. The primary goals of this program are listed below:

1. To observe the incidence of known adverse reactions in children aged 1 to <4 years.
2. To observe the occurrence of unexpected adverse reactions in children aged 1 to <4 years.

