Table 1 Time and Events Table

Procedure	Visit Number			
Visit (Visit Window)	1 ¹ Day1	2 4Ws ±3d	3 12Ws±3d	Early Withdrawal
Informed consent	×			
Demographic data	×			
Medical history	×			
Flixotide 50 µg therapy ²	×	×	×	×

Procedure	Visit Number			
Visit (Visit Window)	1 ¹ Day 1	2 4Ws ±3d	3 12Ws±3d	Early Withdrawal
Concomitant medication	×	×	×	×
Adverse Event ³	×	×	×	×
Serious Adverse event ³	×	×	×	×
Diary card dispense ⁴	×			

1. Visit 1 marks the start of the observational period.
2. Change in drug dosage, discontinuation or resumption and reasons for these changes, and compliance of Flixotide 50 µg therapy.
3. SAEs will be recorded from the time the consent form is signed through Visit 3; AEs will be recorded from the start of Flixotide 50 µg treatment through Visit 3.
4. Paper diary cards will be dispensed at Visit 1 for the parent/guardian of the subject to record Flixotide 50 µg therapy, concomitant medication, AEs and SAEs. The investigator will record the source information in the medical records by asking the parent/guardian of the subject during the follow-up on site or telephone visits.

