8.6.4. Key Elements of Analysis Plan

Safety Analysis

Safety data will be summarized and/or listed for the safety population.

The duration of exposure to Flixotide 50 μ g will be summarized and patient medical history will be listed.

Concomitant medication will be coded using WHO drug and will be summarized by Anatomical Therapeutic Chemical (ATC) classification.

AEs will be coded using MedDRA, and grouped by body system. AEs occurring during administration of Flixotide 50 μ g will be summarized. The number and percentage of subjects experiencing at least one AE of any type, AEs within each body system and AEs within each preferred term will be presented. Separate summaries will be provided for all AEs, drug related AEs, SAEs, and for AEs leading treatment discontinuation.

Analysis methods

No formal hypothesis will be tested in this study. AEs will be listed and summarized descriptively to provide frequency estimate of ADR (=incidence rate of any drug related AEs in safety population) and frequency estimates for any other adverse events reported.

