10.1.1.2. Follow-up of AEs and SAEs

After the initial AE/SAE report, the investigator is required to proactively follow each subject at subsequent visits/contacts. All ADRs and SAEs will be followed until resolution, until the condition stabilizes, until the event is otherwise explained, or until the subject is lost to follow-up. Any follow-up information on a previously reported ADR and SAE must also be reported to vendor and GSK China within the same timeline as initial reports.

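### The only analysis set requires a completed follow-up visit as well as a dose, so a recorded event in a dosed child without such a visit could be left out of the study's tables and listings (minor)

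*Combined protocol and SAP*

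**What the plan says.** Section 8.6.3 defines one analysis set, the safety population. It has two conditions joined by *and*: at least one dose, and that the child "complete one follow up visit, including scheduled or unscheduled visit". A further sentence brings in subjects described as having received retrospectively. It is incomplete and does not say that it waives either condition.

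Section 8.6.4 applies this set: "Safety data will be summarized and/or listed for the safety population". It defines the ADR frequency as the "incidence rate of any drug related AEs in safety population". Its closing paragraph says AEs will be listed and does not name a set.

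Events can be recorded before any follow-up visit. Under Table 1, "AEs will be recorded from the start of Flixotide" treatment, and there are AE and SAE boxes at Visit 1 and at Early Withdrawal. Section 10.1.1 requires ADRs to be reported within 5 calendar days of awareness and SAEs within 24 hours, whatever the visit schedule. The first scheduled follow-up is at 4 weeks (8.5.2).

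Section 8.2.2 says that data gathered before consent is withdrawn are to be used. Section 7 names two primary goals, the second being: "To observe the occurrence of unexpected adverse reactions in children aged 1 to <4 years".

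**The concern.** Inclusion depends on something that happens after dosing. A dosed child whose event is recorded, but who has no later visit that qualifies, leaves the numerator, the denominator and, on the opening sentence of 8.6.4, the listings. This comes from a stated rule, so it cannot be put down to detail left for later.

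The study is small and descriptive, and its main result is one ADR frequency. With so few ADR children expected, one child is visible in the rate. For unexpected reactions, a single case can be the whole finding. There is also an internal conflict: a dosed child whose consent is withdrawn before any follow-up visit has data that 8.2.2 says will be used and that 8.6.3 with 8.6.4 leaves out.

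**Working it through.** **Inputs from the documents.** Planned size is 150 (8.3). The assumed ADR rate is not lower than 1.5%, and 1.68% and 3% are the two source rates cited (8.6.2). The stated probability of seeing at least one ADR is about 90% (8.6.2). No loss rate is given, so losses of 3, 8 and 15 of 150 (2%, about 5%, 10%) are assumed below.

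**1. The plan's own figure.** 1 − (1 − 0.015)^150 = 1 − 0.985^150 = 0.896. The stated figure of about 90% is reproduced.

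**2. Effect of the visit condition on that figure.** With L children excluded, 1 − 0.985^(150 − L):
- L = 3, n = 147: 89.2%
- L = 8, n = 142: 88.3%
- L = 15, n = 135: 87.0%

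The change is small.

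**3. Expected number of children with an ADR.**
- 150 × 1.5% = 2.25, a floor because 8.6.2 says the rate is not lower than this
- 150 × 1.68% = 2.52
- 150 × 3% = 4.5

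**4. How often an ADR child would be among those lost.** If loss is unrelated to ADR and the rate is 1.5%:
- 3 × 0.015 = 0.045
- 8 × 0.015 = 0.12
- 15 × 0.015 = 0.225

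Fewer still would have an event that was also recorded. Loss caused by a reaction would raise these figures by an amount the documents do not give.

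**5. Effect if it does happen once** (illustration, no other exclusions, exact Clopper-Pearson 95% intervals):
- Two ADR children, one omitted: 2/150 = 1.33% (0.16–4.73%) becomes 1/149 = 0.67% (0.02–3.68%).
- Four ADR children, one omitted: 4/150 = 2.67% becomes 3/149 = 2.01%.
- An unexpected reaction seen only in the omitted child: 1/150 = 0.67% (0.02–3.66%) becomes 0/149 = 0% (0–2.45%).

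The intervals shown overlap widely. What changes in the last case is that the reaction is no longer in the results.

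**6. Cost of an all-dosed denominator.** Assume 2 true ADR children, loss unrelated to ADR, and ADRs in lost children unrecorded. The expected all-dosed rate is 2 × ((150 − L)/150) / 150:
- L = 3: 1.31%
- L = 8: 1.26%
- L = 15: 1.20%

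The follow-up-completed rate is 2 × ((150 − L)/150) / (150 − L) = 2/150 = 1.33% for every L.

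**The case against.** The strongest reply is that the affected group is nearly empty. Recording an event needs contact with the family, and contact will often be a visit. Unscheduled visits count, Visits 2 and 3 may be by telephone (8.1), Early Withdrawal is a column in Table 1, and the parent or guardian "must provide reliable contact information which includes home phone or cell phone for the follow up visits". After an initial report, "the investigator is required to proactively follow each subject at subsequent visits/contacts". What clearly remains is an event recorded at Visit 1 itself. Visit 1 is where the drug has been prescribed, and nothing says the first dose is given there. This stands as to size. It does not remove the rule, because the plan never says that an Early Withdrawal assessment or a parent's call is an unscheduled visit.

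The visit condition also has a rationale. A child never contacted after dosing has unknown AE status, and step 6 shows that counting such children as event-free dilutes the rate. This stands, and it is why the current set should be kept.

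The text is not wholly closed either. The last paragraph of 8.6.4 lists AEs without naming a set, and the incomplete sentence in 8.6.3 widens the set in some way. Both leave ambiguity, although the opening sentence of 8.6.4 favours the restrictive reading.

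Three stronger inferences are tempting, and the documents do not support them:
- *Events are lost to the sponsor.* They are not: reporting under 10.1.1 does not depend on the analysis set.
- *The plan itself expects children with a reaction to be lost before any follow-up visit*, because 10.1.1.2 follows events "until the event is otherwise explained, or until the subject is lost to follow-up". That wording only sets an endpoint for following an event. A child lost after Visit 2 fits it and is in the set.
- *The sample-size justification fails.* It does not (steps 1 and 2).

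**Conclusion.** The point holds as a minor one. Read literally, 8.6.3 with 8.6.4 leaves a recorded event in a dosed child with no qualifying later visit out of the tabulated results, and this conflicts with 8.2.2 for a child withdrawn before any follow-up visit. That rests on the opening sentence of 8.6.4 governing the listings and on the incomplete sentence in 8.6.3 not restoring these children.

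The number affected cannot be determined from the documents and is probably very small. With 3 to 15 lost, ADR unrelated to loss and a rate of 1.5%, 0.05 to 0.23 ADR children would be expected among them. The halving of the rate in step 5 presupposes that rare case at the floor rate. A reader might infer a material bias in the ADR rate, but the documents show neither a loss rate nor a link between loss and ADR. The reason to act is narrower: a single unexpected reaction is relevant to a primary goal, and the plan should not be able to leave it untabulated.

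**What to change.** Keep the current safety population for the main ADR rate and amend 8.6.3 and 8.6.4 as follows:
- Every AE and SAE recorded in any child with one or more doses will be listed and counted.
- The number of dosed children without a follow-up visit will be reported, with any events recorded for them.
- The ADR rate will also be shown on all dosed children, as a supporting figure.
- Early Withdrawal assessments and unscheduled telephone contacts count as follow-up visits.
- 8.6.3 is reconciled with 8.2.2 on data gathered before consent is withdrawn, and the incomplete sentence on retrospective receipt is completed.

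The statement on which contacts count would by itself shrink the group further. The listing and the count cover whatever remains.

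The cost is wording, one extra denominator column and one extra table line, with no added patients, visits or data. The drawback is slight dilution of the all-dosed rate if ADRs in lost children go unrecorded: 1.26% against 1.33% with an assumed 8 of 150 lost. That figure should therefore support the main rate and not replace it.

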8.6.4. Key Elements of Analysis Plan

Safety Analysis

Safety data will be summarized and/or listed for the safety population.

The duration of exposure to Flixotide 50 μ g will be summarized and patient medical history will be listed.

Concomitant medication will be coded using WHO drug and will be summarized by Anatomical Therapeutic Chemical (ATC) classification.

AEs will be coded using MedDRA, and grouped by body system. AEs occurring during administration of Flixotide 50 μ g will be summarized. The number and percentage of subjects experiencing at least one AE of any type, AEs within each body system and AEs within each preferred term will be presented. Separate summaries will be provided for all AEs, drug related AEs, SAEs, and for AEs leading treatment discontinuation.

Analysis methods

No formal hypothesis will be tested in this study. AEs will be listed and summarized descriptively to provide frequency estimate of ADR (=incidence rate of any drug related AEs in safety population) and frequency estimates for any other adverse events reported.

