8. RESEARCH METHODS

8.1. Study Design

This is a single arm observational study with no medical interventions. Subjects (children aged 1 to <4 years) information that is pre-defined in the protocol will be collected in the electronic case record form (eCRF). The decision to prescribe Flixotide 50 µg (recommended dosing 50 to 100 µg twice daily inhaled via a paediatric spacer device with a face mask) will not be influenced by whether or not to participate in this observational program.

The observational program will include subjects who have been prescribed Flixotide 50 µg (recommended dosing 50 to 100 µg twice daily inhaled via a paediatric spacer device with a face mask) for appropriate medical use for the first time. The subjects who have been exposed to Flixotide 50 µg, 125 µg and 250 µg previously will not be included.

The maximum program duration will be 12 weeks with 3 visits. Visit1 (Day 1) is the start of the observational program. The follow-up visits will be scheduled at 4 weeks (Visit 2), and 12 weeks (Visit 3). Unless subjects discontinue Flixotide 50 µg treatment or withdraw their consent for continued data collection, subjects will remain in the program until Visit 3.

Visit1 is an on-site visit where subjects have been prescribed Flixotide 50 µg for appropriate medical use. The following procedures/assessments will be performed and recorded during Visit1:

- Obtain written informed consent
- Verification of inclusion criteria
- Obtain the demographic information
- Obtain the medical history
 - Disease history: asthma disease history and other systemic severe disease assessed by investigator.
- Collect concomitant medication use
 - Asthma treatment medication within 30 days prior to Visit 1.
 - Other important medications for severe disease treatment in the past 1 month.
- AEs and SAEs

Visit 2 and Visit 3 are follow-up visit. The follow-up can be conducted on site or by telephone based on the decision made by qualified medical staff. The following assessments will be performed at Visit 2 and Visit3:

- AEs and SAEs
- Collect Flixotide 50 µg treatment information
- Review concomitant medication use

Time and Events Table ([Table 1](#)) provides an outline of the information that will be collected on subjects who have provided consent for data collection according to local ethical guidelines for observational program. Visit 1 is an on-site visit; Visit 2 and Visit 3 are follow-up visits which can be conducted on site or by telephone.

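### AE frequency is planned only as a crude percentage although children leave when they stop Flixotide; this may understate 12-week risk if event-free children stop early, little for ADRs but possibly materially for any AE

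*Combined protocol and SAP*

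**What the plan says.** Section 8.1, like the Abstract, sets how long a child stays: "Unless subjects discontinue Flixotide 50 µg treatment or withdraw their consent for continued data collection, subjects will remain in the program until Visit 3". Twelve weeks is an upper limit: "The maximum program duration will be 12 weeks with 3 visits". Table 1 has an early-withdrawal column in which therapy, concomitant medication, AEs and SAEs are collected.

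Section 8.6.3 puts a child in the safety population after one dose and one follow-up visit, scheduled or not.

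In Section 8.6.4 the events to be summarised are "AEs occurring during administration of Flixotide" 50 µg. The measure is "The number and percentage of subjects experiencing at least one AE of any type", repeated by body system and preferred term, with separate summaries for drug-related AEs, SAEs and AEs that lead to stopping. The ADR frequency is the "incidence rate of any drug related AEs in safety population". Despite the word rate, it has no time in its denominator. Exposure is a separate item ("The duration of exposure to Flixotide" 50 µg is to be summarised). The plan has no rate per subject-time, no time-to-first-event estimate and no rule for children who leave early.

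Table 1 (footnote 3) and Section 10.1.1 have AEs recorded from first dose to Visit 3, with no exception for a child who has already left.

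**The concern.** The numerator follows exposure and the denominator does not. A child who stops at week 4 without an event counts as one whole person, yet was on treatment for a third of the 12 weeks. If such children are numerous, the crude percentage falls below the risk a child would face over 12 weeks of treatment.

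What is at stake is the first goal in Section 7, to observe the incidence of known reactions. A reader given only n (%) cannot tell a low frequency from a short exposure. The any-AE summary matters most, because a given relative shortfall is largest in absolute terms for common events.

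**Working it through.** **The plan's own figure.** Section 8.6.2 uses N = 150 and an ADR rate of 1.5%. P(at least one ADR) = 1 − (1 − 0.015)^150 = 0.896, which agrees with the stated approximately 90%. The calculation treats 1.5% as the risk observed in all 150 children.

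**Assumptions, not from the documents.**
- The event hazard is constant over 12 weeks.
- A fraction f stops at week t, independently of events, and is not observed afterwards.
- The 1.5% is a full 12-week risk.
- The 12-week risk of any AE is 50%, for illustration.

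**Formulas.**
- Hazard per week: h = −ln(1 − p)/12.
- Expected crude percentage: (1 − f)·p + f·(1 − exp(−h·t)).
- Subject-years: 150·[(1 − f)·12 + f·t]·7/365.25.

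**Inputs.** For p = 1.5%, h = 0.00126 per week, so the risk is 0.753% by week 6 and 0.503% by week 4. For p = 50%, h = 0.0578 per week, so the risk is 29.3% by week 6 and 20.6% by week 4.

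**Example.** With 20% stopping at week 6, the ADR percentage is 0.8 × 1.5% + 0.2 × 0.753% = 1.35%. The any-AE percentage is 0.8 × 50% + 0.2 × 29.3% = 45.9%.

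| Assumed stopping | ADR, crude | P(at least one ADR) | Any AE, crude | Subject-years |
|---|---|---|---|---|
| None | 1.50% | 89.6% | 50.0% | 34.5 |
| 20% at week 6 | 1.35% | 87.0% | 45.9% | 31.0 |
| 30% at week 6 | 1.28% | 85.4% | 43.8% | 29.3 |
| 40% at week 4 | 1.10% | 81.0% | 38.3% | 25.3 |

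**Against sampling error.**
- ADRs: the shortfall is 0.15 to 0.40 points. An observed 2/150 (1.3%) has an exact 95% CI of 0.16% to 4.7%, so the shortfall is minor.
- Any AE: the shortfall is 4.1 to 11.7 points. At 50% with 150 children the 95% half-width is 1.96 × √(0.25/150) = 8.0 points, so the shortfall runs from about half of that to more than all of it.

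**Other patterns.** If 10% to 40% stop at times spread evenly over weeks 0 to 12, the ADR figure is 1.43% to 1.20% and the any-AE figure 47.8% to 41.2%. If all events fall in weeks 0 to 4 and 40% stop at evenly spread times, the figures are 1.40% and about 47%. Early clustering of events removes most of the effect.

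**The case against.** The strongest reply is that the plan never names 12-week risk as its target. It aims to describe safety in clinical practice, where stopping is part of use. For risk during actual use, the crude on-treatment percentage is a legitimate estimate, apart from consent withdrawal and loss to follow-up. This stands. But the plan states neither target, so a reader may take the figure for either.

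Four further points stand:
- A child who stops because of an AE is already counted, so the shortfall comes only from event-free children.
- Requiring one follow-up visit removes the earliest leavers from the denominator, which could move the percentage either way.
- The 1.5% is not described as a complete 12-week risk. It lies just below a survey figure (1.68%) whose follow-up is not given, so discounting it again for stopping may double count.
- A rate per 100 subject-years is not a 12-week risk either. With 2 ADRs in 34.5 subject-years it is 5.8 per 100, with an exact 95% CI of about 0.7 to 21. That is why the rate alone would not be enough.

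A reader might infer that only on-drug events will be reported. The text does not support that: Section 8.6.4 also promises frequencies for other reported AEs, and recording runs to Visit 3.

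A reader might also infer that the percentages cannot be set beside the reference data, because Section 6.1 gives 469 subject-years for 703 children. The benchmarks in Section 8.6.2 (3% and 1.68%) are themselves percentages, and the documents give no ADR rate per subject-year. What remains is that the source studies ran for 12 or 52 weeks, so duration should be stated in any comparison.

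Finally, the study is descriptive and already summarises exposure. That limits the weight of the point, but a separate exposure table does not let a reader adjust the AE frequencies.

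**Conclusion.** The point holds conditionally. Follow-up is variable by design, on-treatment AE frequency is planned only as a crude proportion, and the exposure data are not used in it. The proportion may therefore understate 12-week risk if event-free children stop early.

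Under the assumed range of stopping, the effect is small for ADRs (1.5% becomes 1.35% to 1.10%). It could be material for any AE (an assumed 50% becomes about 46% to 38%). Both results rest on a constant hazard, stopping unrelated to events, and discontinuation rates that the documents do not supply.

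A reader might go further and conclude that the 12-week risk is understated as a matter of fact. The documents do not support this, because they give neither a discontinuation rate nor a stated 12-week target. This is a cheap improvement to the reporting. It does not invalidate the planned percentages.

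**What to change.** In Section 8.6.4, keep n (%) as planned and add, for any AE, any ADR and SAEs:

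1. Total on-treatment subject-time and the first-event rate per subject-time, with an exact Poisson 95% CI. State how treatment interruptions count, since Table 1 records discontinuation and resumption.
2. A week-12 cumulative incidence of first event, censoring event-free children at their recorded stop date.
3. The number and timing of discontinuations.

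Say in the table notes that the crude percentage describes events during actual use and the cumulative incidence describes 12-week on-treatment risk. Separately, reconcile the AE window to Visit 3 (Table 1 footnote 3, Section 10.1.1) with exit on discontinuation (Section 8.1), so that it is clear what is observed after a child stops.

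The cost is extra table columns. AE start dates are on the Appendix 1 and 2 forms, discontinuation and resumption are collected under Table 1, and exposure duration is already to be summarised. No added visits or data items are needed for the three estimates. The drawbacks are wide intervals for ADRs, reliance on a constant hazard for the rate, and reliance on non-informative stopping for the cumulative incidence.
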